## 5.7 Withdrawal of Subjects

**2-week trial withdraw.** If a participant fails to walk an average of 2,000 steps/day or exceeds 5,000 steps per day, or cannot sync their Fitbit at the end of the trial period they will be withdrawn. The research staff will call them and thank them participating up to that point and inform them they are not eligible for the full study. The study Fitbit account will be closed, and the research study staff will delete their Fitbit account.

**Active withdraw.** Any participant may at any time notify the Principal Investigator or research coordinator(s) that they no longer wish to participate in the study, and they will be considered withdrawn and will no longer participate in study procedures or activities. We will make every attempt to have a final (remote) study visit with the participant. During the final visit we will encourage the participant to complete the final survey, and we will deactivate their Fitbit account and stop the text/email messages. At this point in time, depending on the arm of the study the participant was randomized to, they will be told the total amount they can expect to receive in the mail, or they will be notified of the non-financial reward(s) they have earned.

**Passive withdraw.** If a participant stops syncing their device, we will encourage them to start syncing it again and we will be available for troubleshooting. If the participant does not sync their device but syncs it before the end of week 24, they will be given all rewards up to that date (reward period week 1-12). If they do not explicitly tell us that they want to withdraw we will keep them in the study. If a participant syncs their device after week 24, they will no longer be eligible for rewards because they have phased out of the study data collection timeframe. After 6 weeks from the Fitbit set-up visit, if the participant has not completed and returned the baseline survey, they will be considered withdrawn.

**Medical withdraw.** At any point in time if a participant experiences a change in their health, is diagnosed with a new condition, gets medical advice to discontinue participation or feels that increasing their exercise is not in their best interest they can choose to withdraw. If a participant has medical questions about their involvement in the study, they can speak with the physician researcher and co-investigator. The physician researcher will review their chart and determine if there is anything that would contra-indicate further participation. Often participants mention their involvement in research to their medical care providers. If any of their medical care providers determine that participating is not beneficial, they may be withdrawn from the study. If this occurs the same withdrawal procedures will be followed for active withdraw. Participants will be compensated for all activities earned to the date of withdraw as outlined in the informed consent document.

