## 4.0 Resources and Personnel

All in person research activities will be conducted at VA Puget Sound Health Care System, Seattle Campus. If the participant activities cannot be done in person, all study activities will occur remotely, over the phone and sending documents through the mail.

Event to trigger a message Weeks 1-12	Messages (text or email)
Reminder	A friendly reminder we are scheduled to complete your Fitbit visit today/tomorrow at _____. If you need to reach us please call [contact].
Baseline period- enrolled	Welcome to the study [If needed] please remember to complete the [baseline/12-week/32-week] survey
Participant day of the week	Acknowledging steps New step goal Financial lottery group: financial winnings & cumulative winnings Non-financial lottery: point winnings & cumulative winnings Loss-framed: Start of week total, updated daily (ideal), weekly minimum
Throughout the study	1 text a week encouraging participants. Day will be random. Reminders (surveys, syncing, return Fitbit (if early withdraw), return postcards, return advice)

Messages week 12-24	Message
Participant day of the week	Message acknowledging steps, encouragement to continue, maintaining gains
Week 12 & 24	Reminder to complete survey, with \$25 compensation
End of week 24	Thank you for participating, time & effort was/is important

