The payments for the enrollment visit, surveys and interview payments will be processed the same week the participant earns them. Participants will earn \$25 for completing the enrollment visit (Consent visit), Fitbit set-up visit, baseline survey, week 12 survey, week 24 survey and interview (if selected). For completing the basic study procedures, visits and surveys, participants will earn up to a total of \$150 if they complete all activities. These payments will be sent out as they are earned. All participants will be paid via direct deposit or electronic gift card. We have tentatively added in the process to vendorize Veterans at the beginning of the study. With the extensive payment issues experienced in prior studies we do not want to further delay any participants receiving payment. We are also adding in statements throughout the participant documents that we cannot guarantee they will be paid. While this is less than ideal, the research study staff has no method to ensure the Veteran is paid at all, appropriately or timely.

The financial rewards from the lottery and the loss-framed groups will be received as one payment. Research coordinators will process all their earnings after week 12. We are doing this to minimize confusion about receiving the correct amount of money. At week 12, participants will know exactly how much money they have earned.

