### **Surveys:**

The participants will need to complete a baseline survey (appendix 6) and follow-up surveys at weeks 12 and 24. The participants will be emailed/texted a link to complete the survey through Qualtrics. The participant will need to complete the baseline survey before finding out what group they are in. Under very rare circumstances if the participant is unable to complete the survey through Qualtrics we will offer the participant the opportunity to complete the survey over the phone with a research coordinator or completing a paper survey. Due to mailing issues, we will strongly encourage the phone survey option. The participant will receive the Qualtrics link after they have been consented and before the Fitbit visit. If the participant still has not completed the survey

by the Fitbit call, we will encourage the participant to complete the survey over the phone. If the participant completes the baseline survey through Qualtrics or over the phone, we will tell them what randomization group they are in and what that means for them. If the participant declines the survey over the phone, we will need their paper copy returned prior to starting the study. Once we receive the paper survey, we will call them to tell them what group they are in and their baseline week start date. They will be instructed to complete the mailed follow-up surveys as soon as possible during week 12 and 24 (appendix 6). The surveys will be completed either through the Qualtrics link or over the phone. Surveys collected over the phone will be recorded either in Excel or the study Access database in the study folder on the J:drive. Once mailed surveys are returned study staff will manually enter survey responses into either the Excel file or the Access database. Another study coordinator will cross check recorded responses to the paper surveys to ensure accuracy.

The survey is comprised of a variety of different measures that account for the secondary outcomes. The secondary outcomes are self-efficacy, intrinsic/extrinsic motivation and mental health.

Self-efficacy: Measured using the Exercise Self-Efficacy Scale at baseline, week 12 and week 24 (McAuley E 1993). This measure has respondents indicate how confident they are they could exercise five times per week at moderate intensity for thirty minutes or more given various conditions. This scale ranges from 0 (not confident) to 10 (very confident).

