Intrinsic/extrinsic motivation: Measured using the Motivation for Physical Activity Measurement (MPAM) at baseline, week 12 and week 24 (Frederick CM 1993). This assessment measures the reasons and motivations for participating in physical activity. The assessment has the subject indicate why they exercise given various reasons and has the subject rate them on a scale 1 to 5. 1 indicates *it is very true for me* and 5 indicates *very untrue for me*.

Mental Health: Measured using the PHQ-8 depression scale at baseline, week 12 and week 24. The rating for this measure asks questions for how often during the past 2 weeks participants bothered by various events. The rating goes from not at all (0 on the scale), several days (1), more than half the days (2), nearly every day (3).

Additional measures that will be used include sociodemographics (from the VA survey of Health Experiences SHEP and Federal Reserve Board Survey of Household Economics and Decision Making), ENRICH Social Support Instrument (ESSI), Perceived Stress Scale, PROMIS sleep disturbance short form ((PHQ) and PROMIS Cooperative Group), Importance of Money Scale (IMS, Franzen and Mad), Loss Aversion (Gachter, Johnson and Herrmann), PROMIS Global Health Scale. These instruments are used to gather demographic data and how much social support and daily interaction the participant has with others. All of these assessments will be presented in the form of a cohesive survey, where responses are recorded based on a scale. Participants will select the response on the scale that most closely matches their life on the day they take the assessment.

Participants will be able to skip any survey responses that they prefer not to answer. All of the surveys are included in Appendix 6.

Main Study, weeks 1-24:

To participate, participants will be instructed to wear their Fitbits daily. Participants will need to open the Fitbit app on their phone and sync the Fitbit with the app on most phones. Participants will receive text message and/or emails with appropriate study updates. These updates will

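### Participants who withdraw are asked for the final survey at the withdrawal visit, after which the plan no longer offers them the week-24 survey that supplies the secondary outcomes

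*Combined protocol and SAP*

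**What the plan says.** **Schedule.** Section 5.5 (Surveys) states: "The participants will need to complete a baseline survey (appendix 6) and follow-up surveys at weeks 12 and 24". It adds that "The survey is comprised of a variety of different measures that account for the secondary outcomes", and then: "The secondary outcomes are self-efficacy, intrinsic/extrinsic motivation and mental health". Each of the three scales has the same times; for mental health the wording is "Measured using the PHQ-8 depression scale at baseline, week 12 and week 24". The survey normally arrives as an emailed or texted Qualtrics link, with phone or paper as a fallback.

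**Withdrawal.** Under Active withdraw in section 5.7, a participant may leave at any point, and staff try to hold a remote final visit. There, "During the final visit we will encourage the participant to complete the final survey, and we will deactivate their Fitbit account"; the same sentence also stops the texts and emails. The participant takes no further part in study procedures. Medical withdraw follows the same steps when a care provider judges participation not beneficial. Under Passive withdraw, someone who merely stops syncing stays in the study.

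**Interventions.** Rewards cover weeks 1-12 (section 5.7). The advice letter goes out in week 13 and the postcards in weeks 13, 17 and 21 (section 5.1).

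**Analysis.** Section 5.6 deals with step counts only. It gives no model for the survey scales, no window for week 24 and no rule for a survey taken at withdrawal.

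**A stray time point.** A message template in section 4.0 reads "please remember to complete the [baseline/12-week/32-week] survey". The second message table in the same section has a row for weeks 12 and 24, "Reminder to complete survey". Section 5.2 pays for "baseline survey, week 12 survey, week 24 survey and interview (if selected").

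**The concern.** The withdrawal procedure changes what is collected. A person who leaves in week 5 may give a survey in week 5 and is then not approached at week 24, even if willing to answer a short web questionnaire. The week-24 score is lost for a reason unrelated to whether it could have been obtained.

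The survey collected in its place answers a different question. Aim 1 (section 3.0) says that factors 2 to 4 are meant to sustain effects once incentives end. A survey before week 13 comes before the advice letter and all postcard mailings, and it cannot show how a participant fares after the rewards have stopped. It is nevertheless called the final survey, and the plan has no label or date rule that would stop an analyst from filing it with the week-24 scores. If withdrawal differed between the levels of a factor, that filing would also bias the comparison.

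**Working it through.** **1. How many follow-up surveys the plan schedules.** The only figure in the plan that depends on this is the $318 maximum for the loss-framed group (section 5.1). Twelve weeks at $14 and the six $25 activities in section 5.2 (consent visit, Fitbit visit, baseline survey, week-12 survey, week-24 survey, interview) give

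12 × 14 + 6 × 25 = 168 + 150 = $318.

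The figure reproduces. A further paid survey at week 32 would make it $343. The sum shows that there are two follow-up surveys. The payment list, the three scale definitions and the reminder row show that they fall at weeks 12 and 24.

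**2. How many participants could be affected.** Inputs: 128 participants and 10% planned loss (section 5.6); 4-7% loss in the earlier trials cited there.

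- Upper bound: 128 × 0.10 = 12.8, about 13 in all and 6.4 per factor level of 64. It is reached only if every loss is an active or medical withdrawal; people who silently stop syncing remain in the study.
- In weeks 1-12, if withdrawals are spread evenly over 24 weeks (assumption): 12.8 × 12/24 = 6.4 in all, 3.2 per level, or 5%. The possible range is 0 to about 13.
- At 4-7% loss: 5.1 to 9.0 in all, of which 2.6 to 4.5 fall in weeks 1-12 on the same assumption.

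**3. Cost if these week-24 scores are simply missing.** The standard error of a two-level contrast is proportional to √(2/n). Going from 64 to 57.6 per level multiplies it by √(64/57.6) = 1.054, an increase of about 5% at the upper bound.

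**4. Cost if withdrawal surveys were filed as week 24.** The plan does not prescribe this; it is a what-if.

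- Shift in a level mean = fraction affected × difference between the early score and the true week-24 score. With an assumed difference of 0.25 to 1.0 SD, the shift is 0.01 to 0.05 SD at 5% affected and 0.03 to 0.10 SD at 10%.
- A factor contrast is biased in this way only if withdrawal differs by level. Assuming a 10-point difference (15% against 5%) and a 0.5 SD score difference, the bias is 0.10 × 0.5 = 0.05 SD. The contrast's standard error is √(2/64) = 0.177 SD, so the bias is 0.28 of a standard error.
- For the advice letter, an early survey carries no effect, so an effect d shrinks to 0.95d at 5% affected and 0.90d at 10%. Take a two-sided alpha of 0.05 (assumption) and an effect with 80% power at 57.6 per level: d = (1.960 + 0.842) × √(2/57.6) = 0.522 SD. Power becomes 78.1% (0.95d, n = 60.8) or 75.7% (0.90d, n = 64).

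**The case against.** The strongest reply is that the plan is silent on scoring. It speaks of a week-12 and a week-24 survey and never equates the withdrawal survey with the latter. That stands. A reader might infer from the word final that reward-period surveys become week-24 scores; the documents do not support this, and step 4 above is only a what-if. The silence does not extend to collection, however: section 5.7 does end contact and messages at withdrawal.

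Other tempting readings also fail.

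- *The final survey has three competing time points.* Week 32 appears once, in a bracketed placeholder, against consistent use of week 24 elsewhere. It also falls well after rewards end, so it could not produce a reward-period score.
- *An early survey carries nothing of the postcard factor.* That arm writes its commitment statements before mailing starts in week 13, and the control arm does not, so part of that contrast is already in place. Only the advice letter is wholly absent.
- *An early survey is taken with rewards running.* This is true of the calendar only. The participant is leaving and is told the earnings at that visit.
- *The plan's power is undermined.* No power is claimed for the secondary outcomes, and section 5.6 gives no numerical alpha. The 75.7% case needs every loss to be a withdrawal before week 13 with a completed survey that is then misfiled.

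Finally, the stakes are limited. The primary outcome is steps, and the Aim 3 panel's listed criteria do not include the survey scales.

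**Conclusion.** The point holds as a gap in data collection. Participants who withdraw actively or on a care provider's advice are asked for the final survey in whatever week they leave and, as written, are not offered the scheduled week-24 survey. When they leave before week 13, what they give does not measure the post-incentive state, and the plan neither uses it as the week-24 score nor sets it apart.

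The size is modest: at most about 13 of 128 participants at the planned 10% loss, and about 6 in weeks 1-12 if withdrawals are evenly spread. Only secondary outcomes are touched; any bias in a factor contrast from mistimed scores needs both misfiling and withdrawal that differs by level, neither of which the documents establish. This is a cheap improvement, not a flaw that threatens the trial's main conclusion. The week-32 entry is clerical.

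**What to change.** 1. In section 5.7, add one question at the final visit: will the participant still accept the scheduled week-12 and week-24 survey links that remain, each with the existing $25 payment? For those who agree, exempt these links from the stop on messages. Those who decline are not contacted again.
2. Record the date and study week of any survey taken at the withdrawal visit, hold it as a separate withdrawal time point, and state in section 5.6 that it is not used as the week-24 score.
3. In the section 4.0 message template, change the week-32 placeholder to week 24, to match the rest of the plan.

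**Cost.** A wording change and one question, plus at most about 13 × 2 = 26 links and 26 × $25 = $650 in payments of a kind that section 5.2 already plans. Some participants will decline or not reply, so some week-24 scores will stay missing. The first change must be in place while participants are being followed, because a survey not offered at week 24 cannot be recovered later.

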## 6.0 Reporting

Participant reports: If a participant reports an unanticipated problem, we will immediately report it to the Principal Investigator. If it is a serious event, we will immediately report it to the IRB. If it is regarding subject payment we will track the issues in our study payment folder on the J:drive and

correspond with the R&D payment staff accordingly. All protocol deviations will be immediately reported to the IRB using the report of problems form.

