We are not doing any screening for a participant being illiterate or having limited or no English proficiency. We are only recruiting Veterans. If English is a Veteran's second or third language, we think they will be fully able to participate. We are also not screening for literacy because that is highly subjective, and we do not believe will impact someone's ability to understand the study. If a potential participant does not respond to our letter, a research coordinator will call them. Every aspect of the study will be explained in a variety of modalities including written (in the enrollment packet) and verbally. Participants and potential participants are free to not enroll or withdraw from the study at any time. We are including these groups because after study team conversations we do not believe this research study exposes these groups to any additional risk. The goal of this study is to increase participants' daily step counts in inactive persons. Increasing step count is a free and relatively easy health behavior that has a positive impact on all individuals regardless of socioeconomic status, educational attainment, or language.

All potential study participants will go through the study screening (CDW, medical record screen and phone screening). All participants will have ample time to ask any questions and go over all study procedures. Potential participants and enrolled participants are free to discuss the study with whomever they chose to make an informed choice about deciding to participate.

The health intervention itself poses no undue risks. Walking is the safest form of physical activity. The risk of minor injury is 0.2 per 1,000 hours of walking. These risks include falls, dehydration, blisters, glycemic control, angina, and worsening of breathing and blood pressure changes. The risks of remaining sedentary out-weigh the risks of adverse events associated with walking. The Physical Activity Guideline Committee 2018 report states that “adding a small and comfortable amount of walking, such as 5 to 15 minutes 2 to 3 times per week, to one’s usual daily activities has a low risk of musculoskeletal injury and no known risk of sudden severe cardiac events.” We put in place three safeguards in this study.

- 1) First, we screen Veterans for an ability to walk 20 minutes without problems (self-report).
- 2) Second, we ask if the potential participant thinks they will benefit from walking more.

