- 3) Third, we make Veteran-specific step goals based on baseline step counts. Each week Veterans will be incentivized for increasing step counts per day by 15% over the previous week’s daily average. For a person with 2,000 steps/day at baseline, this represents an additional 300 steps, or roughly 3 minutes of walking per day. The maximum number of steps any participant will be asked to walk is 7,000 steps per day. If the participant reaches the maximum number of steps per day prior to the end goal at week 12, they will still be eligible for all prizes depending on what group they are in until they reach the maintenance phase at week 12. Once they hit 7,000 steps they will have a goal of 7,000 steps per day until the end of the study. No participants will ever have a goal of >7,000 steps per day.

There will be minimal risks to the participants responding to the study questionnaires (screening and surveys). The screening (appendix 5), surveys (appendix 6), including health history questionnaires, could potentially induce stress secondary to invasion of privacy. Although unlikely, some respondents may find some questions intrusive or offensive. Participants are free to skip any questions they do not wish to answer. Participants will be given a schedule of surveys and will be free to withdraw from the study at any time without penalty or loss of any incentives they have already earned.

All medical centers are required to track the amounts paid to patients during a year. If the amount is \$600 or more, the institution is required by the Internal Revenue Service (IRS) to issue a form 1099MISC to the participant and send a copy to the IRS. This is reported as “miscellaneous” income to the IRS. This amount could have the potential to change Veterans’ eligibility for social services in the coming tax year.

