The medical record screen will be checked to confirm the individual is a Veteran, confirm their age, 50-69.25, and screen negative for: behavioral flag, active psychosis/mania, diagnosis of dementia/Alzheimer's, suicidal or homicidal ideation, presently in the MOVE! Program or pregnant. If the potential participant has diabetes, we will screen their chart to see if they have a diabetic foot ulcer or peripheral neuropathy. Participants with either condition will be excluded. Participants in hospice or end of life care or who are/have been hospitalized in the past 3 months will be excluded. Veterans living in a nursing home, assisted living facility, or group home will be excluded. If data from the CDW data pull is missing or incomplete, we will validate the questionable measure from the medical record. Potentially eligible participants will be mailed a letter describing the study (Appendix 15) and either a self-addressed postcard (Appendix 11) or a QR code that directs them to a Qualtrics survey for them to indicate if they are interested or not (or both a postcard and a QR code). If patients do not opt-out, research staff may telephone patients and screen interested patients for eligibility. Potential participants will be asked a variety of questions to determine eligibility. The full screening questionnaire is included in this submission (Appendix 5). Alternately, the medical record screen may also be conducted after the mailings are sent, with screens only conducted for Veterans who reply with an "interested" response and/or for Veterans who do not respond. The option of conducting the screens after the mailings streamlines the process and allows study staff to prioritize those who are interested in

participating. Should a Veteran indicate interest and then “fail” the medical record screen, they will receive either a letter in the mail or a phone call to inform them. With this method it is likely that not all Veterans who receive recruitment letters will ultimately be contacted about their participation, though we will ensure all Veterans who explicitly indicate interest will be contacted.

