**Exclusion:**

- Not a Veteran of the U.S. Armed Services: We only want to recruit Veterans. We are aware there are non-Veterans that have VA medical records, therefore only Veterans will be recruited.
- Currently in the MOVE! Program. We do not want to enroll participants that are in the MOVE group because group dynamics may be adversely impacted particularly if a participant is receiving incentives.
- Blind: participants will need to be able to read the value on their fitbit and the text messages/emails.
- Highly physical active according to self-report.
- Inability to walk 20 minutes without pain (self-report).
- Diabetic foot condition (ulcer or peripheral neuropathy): We do not want to encourage any activities or increases in activity that could cause harm.
- Dementia/Alzheimer's/cognitive impairment: Potential participants need to fully able to understand the study and what they are voluntarily choosing to participate in.
- Metastatic cancer, end-stage renal disease, hospice, palliative care, heart failure, undergoing chemotherapy, radiation or hemodialysis, have had or are on the list for an organ transplant: We do not want to recruit anyone that is battling a potentially life-threatening condition.
- Implanted cardiovascular device such as defibrillator or ventricular device
- Active psychosis/mania/behavioral flag: We are not able to accommodate potential participants with these conditions or behaviors.
- Pregnant women: We are excluding pregnant women because it is highly unlikely, we will have a 50-year-old plus, inactive female Veteran interested in participating in this study.
- Homeless or housing insecure: We will only exclude individuals experiencing homelessness or housing insecurity if they do not have a way to get mail or charge electronic devices.
- Has a paid caregiver that provides >50% of daily living activities, lives in a nursing home, assisted living facility or group home: Someone that has a caregiver for >50% of daily living activities is likely either medically complex or ill. We understand that many medical conditions and interpersonal relationships can be strained with additional tasks and activities. We do not want this study to interfere with caretaking or this relationship. Individuals that exhibit threatening, violent or otherwise troubling or inappropriate behavior during the screening phone call or consent visit will be excluded from this study.

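### For harms, Section 6.0 waits for a participant to volunteer a problem; the visible plan schedules no question on the foreseen walking harms and no routine route to the physician researcher

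*Combined protocol and SAP*

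**What the plan says.** Section 6.0 (Reporting) is one short paragraph. Its route for harms begins "If a participant reports an unanticipated problem, we will immediately report it to the Principal Investigator" and continues "If it is a serious event, we will immediately report it to the IRB". Payment problems are dealt with under the same heading. Protocol deviations go to the IRB separately, without needing a participant's report.

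The risk text in Section 5.1 names the harms of walking in advance: "These risks include falls, dehydration, blisters, glycemic control, angina, and worsening of breathing and blood pressure changes". It gives one rate: "The risk of minor injury is 0.2 per 1,000 hours of walking". It then says "We put in place three safeguards in this study". These are a screen for walking ability, a question on expected benefit, and individual step goals. The goals are capped: "No participants will ever have a goal of >7,000 steps per day".

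Section 5.7 (Medical withdraw) lets a participant with a change in health choose to leave. A participant with medical questions can speak with the physician researcher, who reviews the chart. A participant's own provider may also prompt withdrawal.

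**The concern.** The plan foresees specific harms, but its reporting route starts only when a participant speaks up, and the term used for the trigger is not defined in the visible text. The person best placed to judge chest pain, a fall or a glycemic problem is the physician researcher, who is not named in Section 6.0. The two follow-up surveys, the messages and the final withdrawal visit could each carry a brief question on harms at almost no cost, and none is described as doing so.

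What is at stake is timely clinical attention to an individual, and a basic record of harms for the panel that will choose components for the next phases. The comparison of step counts is not at stake.

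**Working it through.** The plan states no figure for expected harms, so there is none to reproduce. The main check sets the text side by side; the arithmetic only gives scale.

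**1. Contacts during follow-up, as described**

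| Contact | Described content | Asks about the listed harms? |
|---|---|---|
| Messages (4.0, 5.5) | Steps, goals, rewards, encouragement, syncing, survey reminders; the invitation to call concerns syncing trouble | No |
| Week-12 and week-24 surveys (5.5) | Self-efficacy, motivation, PHQ-8, stress, sleep, social support, global health and others | No item listed |
| Stopped syncing (5.7) | Encouragement and troubleshooting | No; no reason asked |
| Final withdrawal visit (5.7) | Final survey, account closure, messages stopped, rewards | No |
| Medical withdrawal (5.7) | Chart review or withdrawal | Starts with the participant or provider |

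The three safeguards in Section 5.1 are two screening questions and the goal rule, so none is a symptom question during follow-up. The Aim 2 interviews come after week 24, concern acceptability and reach only selected participants.

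**2. Expected minor injuries from added walking**

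Inputs from the documents:
- 128 participants
- 24 weeks
- 100 steps per minute (Section 2.0)
- 0.2 minor injuries per 1,000 hours, goals 15% above the previous week's average, and a cap of 7,000 steps (Section 5.1)
- baseline of 2,000 to 5,000 steps (Section 5.2)

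Assumptions: participants achieve a fraction *a* of each weekly goal increase in weeks 1-12, and hold the week-12 level to week 24.

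- Goal = min(7,000, 1.15 × previous average); new average = previous + *a* × (goal − previous).
- Hours = N × 168 days × mean extra steps per day / 100 / 60; events = hours × 0.2/1,000.

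| Baseline | *a* | Mean extra steps/day | Hours | Expected injuries |
|---|---|---|---|---|
| 2,000 | 0.10 | 299 | 1,070 | 0.21 |
| 3,500 | 0.25 | 1,463 | 5,244 | 1.05 |
| 5,000 | 1 | 1,932 | 6,923 | 1.38 |
| 2,000 | 1 | 3,982 | 14,272 | 2.85 |

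For the last row, 128 × 168 × 3,982 / 6,000 ≈ 14,272 hours, and × 0.0002 gives 2.85. If the 10% loss to follow-up in Section 5.6 contributes nothing (N = 115.2), the four results become 0.19, 0.94, 1.25 and 2.57.

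With every goal met, the goal reaches 7,000 in week 3 from a baseline of 5,000 and in week 9 from 2,000. That leaves 22 and 16 weeks, respectively, at the top goal.

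**3. Would survey items sharpen an estimate?**

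With no event among *n* people, the one-sided 95% upper limit is (1 − 0.05^(1/n)) / capture, where capture is the assumed share of events that become known.

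- Asked, n = 115, full recall: 2.6%.
- Asked, 80% response (n = 92), 75% recall: 4.3%.
- Asked, 60% response (n = 69), 75% recall: 5.7%.
- Not asked, n = 115, capture 50%: 5.1%; capture 25%: 10.3%.

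The ranges overlap, so no gain in precision can be claimed. The surveys are also 12 weeks apart, so their items would help completeness but not prompt detection.

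**The case against.** The strongest reply concerns how the rule would be read. A reader might infer that a reported fall or angina would be dropped because it was anticipated. The documents do not support that. The paragraph covers participants' reports in general, and payment problems, which Section 5.2 itself foresees, sit under the same heading. Staff therefore probably take the term broadly, and nothing says a reported harm would be withheld.

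A reader might also infer that participants are never asked about harms. That goes too far as well. Section 5.1 describes the screening (Appendix 5) and surveys (Appendix 6) as including health history questionnaires, and their content is not in the supplied text. The consent form, study overview, message appendix and the IRB's problem form are also unseen. They may hold reporting instructions or definitions, so the lack of definitions in Section 6.0 is not a defect in its own right.

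Other protections are real. Section 5.4 excludes heart failure, diabetic foot conditions, pain on a 20-minute walk, and "Implanted cardiovascular device such as defibrillator or ventricular device". Section 5.2 adds: "Participants in hospice or end of life care or who are/have been hospitalized in the past 3 months will be excluded". Because each goal follows the previous week's average, someone who slows down is given a lower goal, at least until 7,000 is reached. Section 5.7 gives a symptomatic participant a named clinical contact.

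Two things remain. Every visible route for harms still needs the participant or a provider to start it. And Section 6.0 does not bring in the physician researcher, even once a symptom has been reported.

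**Conclusion.** The point holds as a minor, inexpensive safety improvement. For harms, Section 6.0 depends on volunteered reports sent to the Principal Investigator and, if serious, to the IRB. The visible text schedules no question on the foreseen harms in weeks 1-24. It sends a symptom to the physician researcher only when the participant raises a medical question.

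The scale is small: about 0.2 to 2.9 expected minor injuries, a range set by the assumed goal attainment. That rate covers minor injury only, so it says nothing about angina or glycemic events. The case rests on routing and does not depend on the count. The half about scheduled questions falls away if Appendix 6 already contains harm items; the half about routing to the physician researcher would remain. The primary outcome and its analysis are unaffected.

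**What to change.** - **Section 6.0:** make the trigger any participant-reported fall, injury, symptom listed in Section 5.1, emergency visit or hospitalisation, whether anticipated or not. Send it to the Principal Investigator and the physician researcher. Serious events still go to the IRB.
- **Section 5.5:** unless Appendix 6 already has them, add a short harm item set, identical in all 16 groups, to the week-12 and week-24 surveys and the final withdrawal visit. If Appendix 6 has them, name them in the section.
- **Section 5.7:** ask those who withdraw or stop syncing whether the reason is health-related.
- **Reporting:** tabulate events descriptively, with no claim of added precision.

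The cost is slightly longer surveys, some calls about minor complaints and an IRB amendment. No new visits or staff are needed.
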